## 12.5 Handling of Missing Data

All data obtained in evaluable subjects/eyes will be included in the analysis. No imputation for missing values will be carried out for the effectiveness analyses.

## 12.6 Safety Analyses

The safety endpoints are:

- AEs
- Biomicroscopy findings
- Device deficiencies

There are no safety hypotheses planned in this study. The focus of the safety analysis will be a comprehensive descriptive assessment of occurrence of adverse events as well as the other listed parameters.

All AEs occurring from the time a subject signs informed consent to study exit will be accounted for in the reporting. Safety analyses will be conducted using the safety analysis set on a treatment-emergent basis. Descriptive summaries (frequencies and percentages) for ocular and nonocular AEs will be presented by Medical Dictionary for Regulatory Activities

Preferred Terms. AEs leading to study discontinuation and SAEs will be identified. Individual subject listings will be provided, as necessary.

Individual subject listings will be provided for AEs that occur after signing informed consent but prior to exposure to IP.

[figure not shown]
Each biomicroscopy parameter will be tabulated by its grade. For each biomicroscopy parameter, counts and percentages of eyes that experience an increase of  $\geq 2$  grades from baseline (last assessment prior to study lens exposure) to any subsequent visit will be presented. A supportive listing will be generated which will include all biomicroscopy data from all visits within the same period for those eyes experiencing the increase.

[figure not shown]
Two listings for device deficiencies, prior to exposure to study contact lenses and treatment-emergent, will be provided. Additionally, each device deficiency category will be tabulated.

No inferential testing will be conducted for the safety analyses.

## **12.7 Interim Analyses and Reporting**

There are no plans to conduct an interim analysis and no criteria by which the study would be terminated early based upon statistical determination.

## 13 DATA HANDLING AND ADMINISTRATIVE REQUIREMENTS

### 13.1 Subject Confidentiality

The investigator must ensure that the subject's identity is kept confidential throughout the course of the study. In particular, the investigator must keep an enrollment log with confidential identifying information that corresponds to the subject numbers and initials of each study participant. The study sponsor may collect a copy of the enrollment log ***without any directly identifying subject information.***

The study sponsor may share patient-level data collected in this trial with qualified researchers to help facilitate product development or enhancements in research that is not directly related to the study objectives. The Informed Consent explains this to the study subject.

### 13.2 Completion of Source Documents and Case Report Forms

The nature and location of all source documents will be identified to ensure that original data required to complete the CRFs exist and are accessible for verification by the site monitor, and all discrepancies shall be appropriately documented via the query resolution process. Site monitors are appointed by the study sponsor and are independent of study site staff.

If electronic records are maintained, the method of verification must be determined in advance of starting the study.

At a minimum, source documents include the following information for each subject:

- Subject identification (name, sex, race/ethnicity)
- Documentation of subject eligibility
- Date of informed consent
- Dates of visits

- Documentation that protocol specific procedures were performed
- Results of study parameters, as required by the protocol
- IP accountability records
- Documentation of AEs and other safety parameters (if applicable)
- Records regarding medical histories and the use of concomitant therapies prior to and during the study
- Date of study completion and reason for early discontinuation, if applicable

It is required that the author of an entry in the source documents be identifiable. Direct access to source documentation (medical records) must be allowed for the purpose of verifying that the data recorded on the CRF are consistent with the original source data.

Only designated individuals at the site will complete the CRFs. The CRFs must be completed at regular intervals following the clinical study visit schedule. It is expected that all data reported have corresponding entries in the source documents. The principal investigator is responsible for reviewing and certifying that the CRFs are accurate and complete. The only subject identifiers recorded on the CRFs will be subject number, and subject demographic information.

### **13.3 Data Review and Clarifications**

A review of CRF data to the subject's source data will be completed by the site monitor to ensure completeness and accuracy. After the CRFs have been completed, additional data clarifications and/or additions may be needed as a result of the data cleaning process. Data clarifications are documented and are part of each subject's CRF.

### **13.4 Sponsor and Monitoring Responsibilities**

The study sponsor will select principal investigators that are qualified by education, training, and experience to assume responsibility for the proper conduct of this clinical trial.

The study sponsor is financially funding this clinical trial and will compensate the investigator and/or the Institution(s) at which the study is conducted in accordance with a signed clinical trial agreement.

The study sponsor will designate a monitor to conduct the appropriate site visits at the appropriate intervals according to the study monitoring plan. The clinical investigation will be monitored to ensure that the rights and well-being of the subjects are protected, the reported data are accurate, complete, and verifiable from the source documents, and the study

is conducted in compliance with the current approved protocol (and amendments[s], if applicable), with current GCP, and with applicable regulatory requirements.

The site may not screen subjects or perform the informed consent process on any subject until it receives a notification from an appropriate study sponsor representative that the site may commence conducting study activities. Monitoring will be conducted periodically while the clinical study is ongoing. Monitoring methods may include site visits, telephone, written and fax correspondence. Close-out visits will take place after the last visit of the last subject at the site.

A coordinating investigator may be identified by the study sponsor to review and endorse the final study report. In cases where a coordinating investigator is engaged, the study sponsor will select the coordinating investigator based upon their experience, qualifications, active study participation, and their willingness and availability to take on this role.

### **13.5 Regulatory Documentation and Records Retention**

The investigator is required to maintain up-to-date, complete regulatory documentation as indicated by the study sponsor and the investigator's files will be reviewed as part of the ongoing study monitoring. Financial information is to be kept separately.

Additionally, the investigator must keep study records and source documents consistent with the terms of the clinical study agreement with the study sponsor. If the investigator retires, relocates, or for any other reason withdraws from responsibility of keeping the study records, then the study sponsor must be notified, and suitable arrangements made for retention of study records and source documents needed to comply with national and international regulations.

### **13.6 Quality Assurance and Quality Control**

The study sponsor will secure agreement from all involved parties to ensure direct access to all study related sites, source data and documents, and reports for the purpose of monitoring and auditing by the study sponsor, and inspection by domestic and foreign regulatory authorities. Quality control will be applied to each stage of data handling to ensure that all data are reliable and have been processed correctly. Agreements made by the study sponsor with the investigator/institution and any other parties involved in the clinical study will be provided in writing as part of the protocol or as a separate agreement.

## 14 ETHICS

Investigations are conducted in compliance with Good Clinical Practices; international and national regulations, laws and guidelines; the conditions of approval imposed by reviewing IRBs/IECs or regulatory authorities; and in accordance with the ethical medical research principles outlined in the Declaration of Helsinki and Good Clinical Practices outlined within ISO 14155.

- The SOPs of the study sponsor and contract research organizations participating in the conduct of the clinical study and all other applicable regulations shall apply.
- Notifications and timelines for reporting protocol deviations should be based upon applicable Ethics Committee requirements.

The investigator must ensure that all personnel involved in the conduct of the study are qualified to perform their assigned responsibilities through relevant education, training, and experience. The investigator and all clinical study staff must conduct the clinical study in compliance with the protocol. The investigator is not allowed to deviate from the protocol except to protect the rights, safety, and well-being of human subjects under emergency circumstances. Emergency deviations may proceed without prior approval of the sponsor and the IRB/EC, but shall be documented and reported to the sponsor and the IRB/EC as soon as possible. Deviations from this protocol, regulatory requirements, and/or GCP must be recorded and reported to the Sponsor prior to database lock. If needed, corrective and preventive action should be identified, implemented, and documented within the study records. Failure to implement identified corrective and preventative actions may result in site closure by the sponsor. Use of waivers to deviate from the clinical protocol is prohibited.

Before clinical study initiation, this protocol, the informed consent form, any other written information given to subjects, and any advertisements planned for subject recruitment must be approved by an IRB/IEC. The investigator must provide documentation of the IRB/IEC approval to the study sponsor. The approval must be dated and must identify the applicable protocol, amendments (if any), informed consent form, assent form (if any), all applicable recruiting materials, written information for subject, and subject compensation programs. The IRB/IEC must be provided with a copy of the Investigator's Brochure, any periodic safety updates, and all other information as required by local regulation and/or the IRB/IEC. Any additional requirements imposed by the EC or regulatory authority shall be followed. At the end of the study, the investigator must notify the IRB/IEC about the study's completion. The IRB/IEC also must be notified if the study is terminated prematurely. Finally, the investigator must report to the IRB/IEC on the progress of the study at intervals stipulated by the IRB/IEC.

Voluntary informed consent must be obtained in writing from every subject. The obtaining of consent shall be documented before any procedure specific to the clinical investigation is applied to the subject.

The investigator must have a defined process for obtaining the required consent. Specifically, the investigator, or their delegate, must explain the clinical study to each potential subject and the subject must indicate voluntary consent by signing and dating the approved informed consent form. The subject must be provided an opportunity to ask questions of the investigator, and if required by local regulation, other qualified personnel. The investigator must provide the subject with a copy of the consent form written in a language the subject understands. The consent document must meet all applicable local laws and provide subjects with information regarding the purpose, procedures, requirements, and restrictions of the study, along with any known risks and potential benefits associated with the IP and the study, the available compensation, and the established provisions for maintaining confidentiality of personal, protected health information. Subjects will be told about the voluntary nature of participation in the study and must be provided with contact information for the appropriate individuals should questions or concerns arise during the study. The subject also must be told that their records may be accessed by appropriate authorities and sponsor-designated personnel. The investigator must keep the original, signed copy of the consent (file in subject's medical records) and must provide a duplicate copy to each subject according to local regulations.

The study sponsor assures that the key designs of this protocol will be registered on public databases where required by current regulations, and, as applicable, results will be posted.

## **16 APPENDIX A – Protocol Amendments**

There are no amendments. This is the first version of the protocol.

Clinical Performance Assessment of Two Silicone Hydrogel Daily Disposable Contact Lenses

STUDY ID:

CLX679-C001

STATISTICAL ANALYSIS PLAN

NCT05725317

Statistical Analysis Plan for CLX679-C001

Title: Clinical Performance Assessment of Two Silicone Hydrogel Daily Disposable Contact Lenses

This version of the Statistical Analysis Plan is based on Version 1.0 of the study protocol.

Executive Summary:

Key Objectives:

The Primary objective of this study is to demonstrate noninferiority (NI) in visual acuity (VA) at distance when wearing [REDACTED] contact lenses compared to DT1 contact lenses, after approximately 4 days of wear.

Decision Criteria for Study Success:

Success of this study will be based on demonstration of NI in distance VA with [REDACTED] contact lenses when compared to DT1 contact lenses, at Day 4, using a margin of 0.05 on the logMAR scale.

Table of Contents

Statistical Analysis Plan for CLX679-C001	1
Table of Contents	3
List of Tables.....	4
List of Figures.....	4
1 STUDY OBJECTIVES AND DESIGN	5
1.1 Study Objectives.....	5
1.2 Study Description	5
1.3 Randomization.....	6
1.4 Masking	6
1.5 Interim Analysis.....	7
2 ANALYSIS SETS	7
2.1 Safety Analysis Set.....	7
2.2 Full Analysis Set.....	7
2.3 Per Protocol Analysis Set	7
3 SUBJECT CHARACTERISTICS AND STUDY CONDUCT SUMMARIES	7
4 EFFECTIVENESS ANALYSIS STRATEGY.....	8
4.1 Effectiveness Endpoints	9
4.2 Effectiveness Hypotheses	10
4.3 Statistical Methods for Effectiveness Analyses.....	10
4.3.1 Primary Effectiveness Analysis	10
4.6 Interim Analysis for Effectiveness	11
5 Safety Analysis Strategy.....	12
5.1 Safety Endpoints.....	12
5.2 Safety Hypotheses	12
5.3 Statistical Methods for Safety Analyses.....	12
5.3.1 Adverse Events.....	13
5.3.2 Biomicroscopy Findings.....	13
5.3.3 Device Deficiencies.....	14

7	SAMPLE SIZE AND POWER CALCULATIONS	14
8	REFERENCES	14
9	REVISION HISTORY	15
10	APPENDIX	16

List of Tables

Table 1-1	Study Description Summary.....	5
Table 10-1	Schedule of Study Procedures and Assessments	16

List of Figures

Figure 1-1	Study Design.....	6
------------	-------------------	---

1 STUDY OBJECTIVES AND DESIGN

1.1 Study Objectives

PRIMARY OBJECTIVE

The primary objective of this study is to demonstrate NI in VA at distance when wearing [REDACTED] contact lenses compared to DT1 contact lenses, after approximately 4 days of wear.

[REDACTED]

1.2 Study Description

Key components of the study are summarized in Table 1-1.

[figure not shown]
Table 1-1 **Study Description Summary**

Study Design	Prospective, randomized, [REDACTED] [REDACTED], double-masked, contralateral
Study population	Habitual spherical soft contact lens wearers aged 18 or above, having at least 3 months of contact lens wearing experience, and who wear their habitual contact lenses for at least 5 days per week and at least 10 hours per day. [REDACTED] [REDACTED] Target to complete: 100 [REDACTED] [REDACTED] Planned to enroll: ~110
Number of Sites	~ 7 US
Test Product	[REDACTED] delefilcon A; LID220365)
Comparator Product	DAILIES TOTAL1® spherical soft contact lenses (DT1; delefilcon A; LID006961)
Planned Duration of	~ 4 days total duration (test and comparator):

Exposure	Test Product: 4 (-1/+1) days Comparator Product: 4 (-1/+1) days
Visits	Visit 1: Screening/Baseline/Dispense [Day 1] Visit 2: Day 4 Follow-up/Exit [Day 4 (-1 /+1)]

A study design schematic is depicted in Figure 1-1.

Figure 1-1 **Study Design**

1.3 Randomization

A member of the Randomization Programming group at Alcon who is not part of the study team will generate the randomized allocation schedule(s) for study lens sequence assignment. Randomization will be implemented in the Electronic Data Capture (EDC)/randomization integration system.

Qualifying subjects will be randomized in a 1:1 ratio to receive treatment (lens) in contralateral sequence [REDACTED]

Sequence	EDC/randomization integration system	[REDACTED]
Sequence 1	LID220365(OD)/LID006961(OS)	[REDACTED]
Sequence 2	LID006961(OD)/LID220365(OS)	[REDACTED]

1.4 Masking

This study is double-masked.

1.5 Interim Analysis

There are no plans to conduct an interim analysis and no criteria by which the study would be terminated early based upon statistical determination.

2 ANALYSIS SETS

2.1 Safety Analysis Set

Safety analysis will be conducted using the safety analysis set on a treatment-emergent basis. As such, the safety analysis set will include all subjects/eyes exposed to any study lenses evaluated in this study. [REDACTED]

[REDACTED] Any adverse event (AE) or device deficiency occurring after informed consent and prior to first exposure of the study lenses under evaluation in this clinical protocol will be listed as pre-treatment.

For treatment-emergent safety analyses, subjects/eyes will be categorized under the actual study lens exposed in the corresponding lens sequence.

Adverse events occurring from the time of informed consent but prior to first exposure to study lenses will be summarized in subject listings.

2.2 Full Analysis Set

The full analysis set (FAS) is the set of all randomized subjects who are exposed to any study lenses [REDACTED] evaluated in this study.

2.3 Per Protocol Analysis Set

The per protocol (PP) analysis set is a subset of FAS and excludes all data/subjects that have met any of the critical deviation or evaluability criteria identified in the Deviation and Evaluability Plan (DEP).

3 SUBJECT CHARACTERISTICS AND STUDY CONDUCT SUMMARIES

The following tables will be presented:

- Subject Disposition by Lens Sequence
- Analysis Sets by Lens
- Analysis Sets by Lens Sequence
- Subject Accounting by Lens Sequence
- Demographics by Lens Sequence
- Baseline Characteristics by Lens Sequence [REDACTED]
[REDACTED]
[REDACTED]

Subject accounting and demographics tables will be summarized on the safety, full, and per protocol analysis datasets. Baseline characteristics will be summarized on the full and per protocol analysis datasets.

In addition, the following subject listings will be provided:

- Listing of Subjects Excluded from Protocol Defined Analysis Sets
- Listing of Lens Sequence Assignment by Investigator
- Listing of Subjects Discontinued from Study

4 EFFECTIVENESS ANALYSIS STRATEGY

This study [REDACTED]
[REDACTED] will use the FAS as the primary analysis.

[REDACTED]
[REDACTED]
[REDACTED]

[REDACTED]

Continuous variables will be summarized using the number of observations, mean, SD, median, minimum, and maximum, as well as confidence intervals (CIs) or confidence limits (CLs) where applicable. Categorical variables will be summarized with frequencies and percentages from each category.

All data obtained in evaluable subjects/eyes will be included in the analysis. No imputation for missing values will be carried out for the effectiveness analyses.

[figure not shown]
For all planned inferential analyses, alternative models/methods may be considered, for instance, if convergence cannot be achieved.

A listing of select effectiveness data will also be provided.

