### 12.1 Subject Evaluability

Final subject evaluability must be determined prior to breaking the code for masked treatment (lens sequence) assignment and locking the database, based upon the Deviations and Evaluability Plan (DEP).

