#### 12.2.2 Full Analysis Set

The full analysis set (FAS) is the set of all randomized subjects who are exposed to any study lenses evaluated in this study.

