#### 12.2.3 Per Protocol Analysis Set

The per protocol (PP) analysis set is a subset of FAS and excludes all data/subjects that have met any of the critical deviation or evaluability criteria identified in the DEP.

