## 12.4 Effectiveness Analyses

This study [REDACTED] will use the FAS as the primary analysis set.

[REDACTED]

[REDACTED]

[REDACTED]

[REDACTED]

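### Does the word *evaluable* in the effectiveness data rule put a hidden filter on the primary full analysis set?

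*SAP*

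**What the plan says.** Both documents carry the same data rule. In SAP section 4 it reads "All data obtained in evaluable subjects/eyes will be included in the analysis", and Protocol 12.5 repeats it. In both places the next sentence rules out imputing missing effectiveness data. The rule itself does not mention an analysis set.

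The sets are defined elsewhere:

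- **Primary set.** Protocol 12.4 states that the study "will use the FAS as the primary analysis set"; SAP section 4 agrees.
- **Full analysis set.** Protocol 12.2.2, which has no redaction, reads "The full analysis set (FAS) is the set of all randomized subjects who are exposed to any study lenses evaluated in this study". SAP 2.2 matches it in its visible words.
- **Per protocol set.** Protocol 12.2.3 makes it a subset of the FAS that "excludes all data/subjects that have met any of the critical deviation or evaluability criteria identified in the DEP"; SAP 2.3 says the same.
- **Evaluability.** Protocol 12.1 has it decided from the Deviations and Evaluability Plan (DEP) before the lens-sequence code is broken. The Protocol Glossary counts that plan as part of the clinical investigation plan.

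**The concern.** *Evaluable* is not a casual word here. It is the outcome of a process run under the DEP, and in the visible text that outcome is otherwise used only to remove subjects or data from the per protocol set. When the same word appears in the general effectiveness rule, with no set named, it can look as though the FAS analysis must also pass through the evaluability filter. The safety set is worded without that qualifier: "the safety analysis set will include all subjects/eyes exposed to any study lenses evaluated in this study". The contrast makes *evaluable* look deliberate.

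Study success rests on one noninferiority test in the FAS. If one programmer filtered the FAS by evaluability and another did not, they would build different datasets from the same text, one of them with exclusions made after randomization. SAP section 3 treats the full and per protocol sets as separate datasets, so someone has to program the distinction.

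**Working it through.** **1. Set the texts side by side.**

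| Text | Who it concerns | Does it exclude anyone? |
|---|---|---|
| Protocol 12.2.2, SAP 2.2 | FAS: randomized and exposed | Only those not randomized or not exposed |
| Protocol 12.2.3, SAP 2.3 | Per protocol set | Yes, through the DEP criteria |
| Protocol 12.4, SAP 4 | Names the FAS as primary | No |
| Protocol 12.5, SAP 4 | Evaluable subjects and eyes | No; it says their data go in |

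An analysis of every observed value in the FAS satisfies all four rows. The fourth row contradicts the second only if the reader adds the word *only*. Its position points the other way: in the protocol it is the first line under the missing-data heading, and the no-imputation rule follows. Together the two sentences say to use what was observed and to fill in nothing.

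**2. Reproduce the plan's sample size, to fix the scale.** Inputs (Protocol section 3, SAP section 7): SD of the paired difference 0.0567, margin 0.05, one-sided alpha 0.05. Assumption: true difference 0.

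- Normal approximation, n = [SD × (z(0.95) + z(power)) / margin]²: 7.95 at 80% and 11.01 at 90%, so 8 and 12.
- Noncentral t: N = 10 gives power 0.823; N = 13 gives 0.911 and N = 14 gives 0.930.

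The plan states 10 and 14. The first agrees exactly. The second agrees if 13 is rounded up to an even number for two equal sequences.

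**3. Precision and power at the planned size.** With 100 completers, the one-sided half-width is t(0.95, 99) × 0.0567/√100 = 1.6604 × 0.00567 = 0.0094. With a true difference of 0, power exceeds 0.9999 for any analysed number from 50 to 100. With an assumed true difference of 0.03 it is 0.968 at 100, 0.931 at 80 and 0.792 at 50.

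**4. What a mistaken filter could do to the estimate.** The documents give no rate of non-evaluable subjects, so the following is an assumed range. Of 100 FAS subjects, k are dropped, and their mean test-minus-comparator difference is d logMAR worse than in those kept.

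- Shift in the mean = k × d/100.
- Pooled SD² = [98 × 0.0567² + k(100 − k)d²/100] / 99.
- Unfiltered upper limit with kept mean 0 = shift + 1.6604 × pooled SD/10.
- The two versions disagree when the kept mean is at least 0.05 minus that limit, but below 0.05 minus the filtered half-width, t(0.95, 99 − k) × 0.0567/√(100 − k).

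| k | d | Shift | Share of margin | Unfiltered upper limit, kept mean 0 | Kept means at which decisions differ |
|---|---|---|---|---|---|
| 2 | 0.05 | 0.001 | 2% | 0.0104 | 0.0396 to 0.0405 |
| 5 | 0.10 | 0.005 | 10% | 0.0150 | 0.0350 to 0.0403 |
| 10 | 0.20 | 0.020 | 40% | 0.0337 | 0.0163 to 0.0401 |

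With a kept mean of 0, noninferiority is declared with or without the filter in every row. The assumed gaps are not timid: 0.05/0.0567 = 0.9 and 0.20/0.0567 = 3.5 paired SDs.

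**The case for a change.** The best case for a change is that the sentence is faulty on either reading. If non-evaluable data are also analysed, *evaluable* does no work. If they are not, the primary test carries an exclusion absent from the FAS definition. The rule is the only visible statement on which observed data enter the effectiveness analysis, it bears on the sole success criterion, and one sentence would clear it up. In the extreme row of the table the two versions disagree over a wide band, 0.0163 to 0.0401. Deciding evaluability before unmasking limits choices informed by treatment, but it does not say which eyes are analysed.

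Part of this stands. The wording is loose, and *evaluable* is either redundant or unexplained. The calculation also treats exclusion by subject, where both lenses leave together; it does not cover the removal of single eyes.

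The rest does not carry a change. A redundant word is not a conflict when the set definitions give the answer. The claim that no set is assigned cannot be confirmed either, because lines directly after the FAS statement are blacked out in Protocol 12.4 and SAP section 4, and the DEP may define the term by set or by eye. The wording of the safety set shows nothing about what *evaluable* means for effectiveness. The extreme row needs 10% of subjects excluded with a gap of 3.5 paired SDs, together with a kept mean well away from zero.

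**Conclusion.** No change to the plan follows. This is a gap in wording that an analyst fills sensibly from the plan itself: the FAS is primary, its definition has no evaluability condition, and the DEP exclusions are assigned expressly to the per protocol set. Following those definitions gives a sound primary test.

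The size of a misreading is unknown without the DEP. Under the assumed range it is a shift of 0.001 to 0.020 logMAR. In the middle case it is 0.005, and the decision would differ only if the kept mean lay between about 0.035 and 0.040. Power is not at issue. The conclusion rests on the visible text, on the planned SD of 0.0567 with 100 analysed subjects, and on assumed exclusion rates and gaps. It would need another look only if the DEP were found to apply evaluability to the FAS itself.
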